9.4 Safety Analysis

All treated subjects will be considered evaluable for safety. Skin irritation scores will be reported for any subject who is scored with a 1 or more at any observation (baseline treatment day, post-application/prior to 30 seconds and 10 minutes sampling procedures), in any category for any site.

Adverse events (including post treatment skin irritation scores of 3), will also be summarized. Summary tables will present incidence rates of adverse events by treatment group for all subjects who enter the treatment period. Listings of adverse events will be provided.

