2.3 Safety objectives

Safety will also be evaluated based on the incidence of adverse events reported during the study and assessment of skin irritation ratings from Appendix 17.6.

3 Study Design

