3.3 Endpoints

- Log₁₀ CFU/cm² of skin flora at the groin site before and after each treatment at 30 seconds,
 10 minutes.
- Skin irritation scores (Erythema, Edema, Rash, and Dryness) at each time interval and the incidence of AEs reported during the study.

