8.1 Safety Parameters

The principal measures of safety will be skin irritation scores and the incidence of adverse events reported during the study.

Adverse events will be captured from the time the subject have signed the Informed consent form to the time of subject discharge from the study. Adverse events will be categorized in relationship to the product that was applied to the specific skin site. All local and systemic adverse events observed or reported to the investigator will be evaluated.

The severity, duration, causal relationship to the study product and study procedure, action taken (study related and subject related), study impact, outcome of the event; will be described for all adverse events.

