8.2 Assessment Methods for Skin Irritation

All randomized subjects will be considered evaluable for safety. Skin irritation scores based on the scale from Appendix 17.6 will be reported for any subject who is scored with a 1 or more at any observation (baseline treatment day, clipping/re-clipping and prior/post-application to 30 seconds and 10 minutes sampling procedures), in any category for any site.

Adverse events (including post treatment skin irritation scores of 3), will also be summarized. Summary tables will present incidence rates of adverse events by treatment group for all subjects who enter the treatment period. Listings of adverse events will be provided.

A corresponding rating score for each individual skin condition, for each site will be recorded in the subject's CRF. (See Appendix 17.6, which includes the following four independent evaluation categories: Erythema, Edema, Rash, and Dryness).

If an irritation score of 1 or greater for any individual skin condition prior to the baseline sample collection (at treatment day phase) is assigned, the subject will be excluded from the study (no study treatment will be applied).

If an irritation score of 3 for any individual skin condition at any observation period is assigned, the subject will be discontinued from the study and an adverse event will be recorded. See Section 8.3 (Adverse Events).

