17.6 Skin Irritation Rating Scale

Skin Irritation Scoring System			
Condition	Rating	Description	
	0	No reaction	
Erythema	1	Mild and/or transient redness limited to sensitive area	
Liyenema	2	Moderate redness persisting over much of the product-exposed area	
	3*	Severe redness extending over most or all of the product-exposed area	
	0	No reaction	
Edema	1	Mild and/or transient swelling limited to sensitive area	
Lacina	2	Moderate swelling persisting over much of the product-exposed area	
	3*	Severe swelling extending over most or all of the product-exposed area	
	0	No reaction	
Rash	1	Mild and/or transient rash limited to sensitive area	
110511	2	Moderate rash persisting over much of the product-exposed area	
	3*	Severe rash extending over most or all of the product-exposed area	
	0	No reaction	
Dryness	1	Mild and/or transient dryness limited to sensitive area	
Diyiless	2	Moderate dryness persisting over much of the product-exposed area	
	3*	Severe dryness extending over most of all of the product-exposed area	

^{*} A score of 3 in one or more of the conditions evaluated represents significant irritation and qualifies as an Adverse Event.

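### Irritation scores of 1 and 2 have no planned rate by product, although skin irritation is a named endpoint and a principal safety measure

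*Combined protocol and SAP*

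**What the plan says.** Section 3.3 lists as an endpoint "Skin irritation scores (Erythema, Edema, Rash, and Dryness) at each time interval and the incidence of AEs reported during the study". Section 8.1 gives these scores the same standing as adverse events: "The principal measures of safety will be skin irritation scores and the incidence of adverse events reported during the study". The safety objective in 2.3 also rests on them: "Safety will also be evaluated based on the incidence of adverse events reported during the study and assessment of skin irritation ratings from" Appendix 17.6.

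Scores are collected in full. Section 8.2 states: "A corresponding rating score for each individual skin condition, for each site will be recorded in the subject's CRF". Section 5.1.2.3 requires an assessment before each post-treatment sample, at 30 seconds and at 10 minutes.

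The stated output is narrower. Section 9.4 says: "Skin irritation scores will be reported for any subject who is scored with a 1 or more at any observation". The synopsis and 8.2 give the same rule with slightly different lists of observations: 9.4 includes the Treatment Day baseline, and 8.2 adds clipping. Rates are planned for adverse events: "Summary tables will present incidence rates of adverse events by treatment group for all subjects who enter the treatment period". Score 3 reaches those tables, because 9.4 says "Adverse events (including post treatment skin irritation scores of 3), will also be summarized" and the footnote in 17.6 says "A score of 3 in one or more of the conditions evaluated represents significant irritation and qualifies as an Adverse Event".

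**The concern.** A report confined to subjects with a non-zero score selects on the outcome. Sites that scored 0 appear only if they belong to a subject who scored elsewhere, so the report has no denominator of its own. Three features make it harder to read by product:

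- The trigger is the subject, but each subject receives two of the four products, one on each side.
- Under 8.2 and 9.4 the trigger includes observations made before any product is applied. Section 8.2 excludes a subject scored 1 or more before baseline sampling, with no treatment given, so such a subject would be listed without exposure to any product.
- A score of 0 that is left out looks the same as a score that was never taken.

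Redness, swelling, rash and irritation are among the risks in 7.1. At stake is whether the report shows how often each product produced a mild or moderate reaction, and how precisely that is known when few or none occur. The efficacy endpoint beside it in 3.3 does receive descriptive statistics by treatment and time point (9.3).

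**Working it through.** **Step 1: what each score receives after application.**

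| Score | Recorded by condition and site | Stated output | Rate by product |
|---|---|---|---|
| 0 | Yes (8.2) | Only if the subject scored 1 or more somewhere | None |
| 1 or 2 | Yes (8.2) | Report for the affected subject (synopsis, 8.2, 9.4) | None stated |
| 3 | Yes (8.2) | The same report, plus the adverse event summary (9.4, 17.6) | Yes, through adverse event incidence by treatment group |

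The gap is therefore scores 1 and 2, and the overall proportion scored 1 or more.

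**Step 2: the plan's own numbers.** Inputs are 4 products, at least 50 evaluable sites each (9.2) and 2 sites per subject (3.1). 4 × 50 / 2 = 100 subjects, which matches the 100 in 3.1.

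Fifty is a floor on evaluable sites, not the number treated. Baseline plates incubate for about 72 hours (5.2.2), while products are applied on Treatment Day after baseline sampling (5.1.2.2). Sites that later fail the baseline range have already been treated, and 3.4 provides extra randomization entries to replace them. Treated sites per product may therefore exceed 50, so the efficacy counts cannot serve as the safety denominator.

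**Step 3: what a by-site proportion would show.** The plan gives no irritation rates, so the counts x below are illustrations. The exact (Clopper-Pearson) 95% interval for x of n sites has

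- lower limit: the 2.5% quantile of Beta(x, n − x + 1), or 0 when x = 0;
- upper limit: the 97.5% quantile of Beta(x + 1, n − x), which for x = 0 equals 1 − 0.025^(1/n).

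| Sites scored 1 or more, of 50 | Proportion | Exact 95% interval |
|---|---|---|
| 0 | 0% | 0 to 7.1% |
| 1 | 2% | 0.05% to 10.6% |
| 3 | 6% | 1.3% to 16.5% |
| 5 | 10% | 3.3% to 21.8% |
| 10 | 20% | 10.0% to 33.7% |

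With more treated sites the upper limit for zero reactions falls: 1 − 0.025^(1/60) = 6.0% at an assumed 60 sites, and 1 − 0.025^(1/75) = 4.8% at an assumed 75. No stated output gives these limits.

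**Step 4: what the table could not do.** With 50 sites per product, sites treated as independent and two-sided alpha of 0.05, power for assumed rates of 5% against 20% is about 62%, and for 10% against 30% about 71%. The table would describe; it would not support a claim of equal tolerability.

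**The case against.** The strongest reply is that nothing is lost. Every score is recorded by condition and site, the randomization gives the product on each side, and the report covers every subject with a non-zero score. If the report shows site and product, rates follow by division. Section 9.4 adds that adverse events "Adverse events (including post treatment skin irritation scores of 3), will also be summarized", and the word also can be read as implying that irritation is summarized too. The plan does not exclude a table.

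Much of this stands. A reader might infer that the trial cannot compare irritation between A, B or C and D; the documents do not support that, because the data exist. A reader might also infer that irritation has no rate by product at all; that is wrong for score 3. Nor is a promised comparison missing: 2.3 states no comparison with D, no margin and no test for safety, and non-inferiority to D belongs to efficacy (2.1).

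What does not stand is that the stated rule is enough. It appears three times, and none of the three mentions product, time point or number of sites treated. Division by hand needs a count of treated sites per product, which no planned output supplies, and needs zeros to be told apart from missing scores. Missing scores are possible by design: a score of 3 at 30 seconds leads to discontinuation (5.1.2.3), so the 10-minute score may be absent.

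The adverse event definition in 8.3 is broad and might capture some scores of 1 or 2. The only score the plan names for those tables is 3.

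**Conclusion.** The point holds as a weakness of the planned summary. An endpoint that is also a principal safety measure has no pre-specified, denominator-based rate by product, condition or post-application time for scores below 3. The efficacy conclusions are unaffected, and the rates remain recoverable from the data.

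The size is illustrative only: at 50 sites per product, zero reactions is compatible with a true rate of up to 7.1%, and 5 reactions with 3.3% to 21.8%. These figures rest on an n that is a minimum of evaluable sites, so intervals on treated sites may be somewhat narrower. Each interval treats the sites of one product as independent, which is reasonable because a subject's two sites carry different products. Any contrast between products would have to allow for subjects who contribute a site to both.

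This concerns how scores are summarized. It takes no position on which scores should count as adverse events or lead to discontinuation.

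**What to change.** Keep the listing, and add one descriptive table to 9.4, 8.2 and the synopsis. For each product (A, B, C, D), each condition (erythema, edema, rash, dryness) and each post-application time (30 seconds, 10 minutes), give the number and percentage of treated sites scored 0, 1, 2, 3 and missing. Use all treated sites of that product as the denominator, and give an exact 95% interval for the proportion scored 1 or more. Keep scores from before application out of this table.

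In the same edit, reconcile the safety set: the synopsis and 9.4 refer to treated subjects, while 8.2 and 9.1 refer to randomized subjects. The choice matters here, because a site randomized but not treated would add to the denominator without being able to contribute a post-application score. The differing lists of observations in the synopsis, 8.2 and 9.4 should be aligned too.

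The cost is a sentence or two in three places and one extra table. The scores are already on the CRF by site, so no new data, visits or procedures are needed. The downside is that intervals will be wide and the table must be labelled descriptive.

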9.5 Procedures for Accounting for Missing, Unused, and Spurious Data

Missing microbiological data at 30 seconds, or 10 minutes, such as due to laboratory error or subject lost to follow-up, will be reported as missing and will not be imputed. Inclusion of these subjects in the per-protocol data set will be based on the criteria defined above. Details of any missing data and rationale for inclusion/exclusion in the per-protocol data set will be described in the study report.

10 PI Responsibilities

The PI is responsible for ensuring that this clinical investigation is conducted according to this protocol; protecting the rights, safety, and welfare of subjects; and controlling the study products under investigation. The PI has overall responsibility for the technical conduct of the study, as well as for the interpretation, analysis, documentation and reporting of results, and represents the single point of study control.

11 Monitoring

PDI, as sponsor of this study along with the PI, is responsible for ensuring the proper conduct of the study with regard to protocol adherence and validity of the data recorded on the CRFs. PDI has, therefore, assigned a study monitor to this study. The progress of the study will be monitored by:

- Periodic on-site review
- Telephone communications and e-mail
- Review of CRFs and source documents

The PI will give the PDI study monitor direct access to source documents that support data on the CRFs and make available such records to authorized PDI personnel, quality assurance, IRB/IEC, and regulatory personnel for inspection and/or copying.

12 Quality Control and Quality Assurance

PDI, and the PI are responsible for implementing and maintaining Quality Assurance and Quality Control systems through written SOPs to ensure that this study is conducted and data are generated, documented and reported in compliance with the protocol, GCP and regulations cited in Section 14 of this protocol. Study monitoring may be carried out to accomplish this.

13 Audits and Inspections

If the study is selected for audit by the Sponsor or if there is an inspection by the appropriate Health Authorities, then the PI and her team will make themselves available during the visit. The PI must agree to the inspection of all study related records and give the auditor/inspector direct access to source documents for verification of data on CRFs. The subject's anonymity must be safeguarded and data checked during the audit remain confidential.

As soon as the PI is aware of an upcoming inspection/audit by the Health Authorities, she will promptly inform PDI. As agreed with the PI, PDI personnel might be present at the site during the inspection.

14 Ethical and Regulatory Standards

The study will be conducted in compliance with this protocol, the regulatory guidelines of the US FDA regulations, 21 CFR 50 (Protection of Human Subjects), 56 (IRB), the ethical principles of the Declaration of Helsinki, the ICH-GCP Guidelines as currently amended, and all applicable SOPs of ER

The study will start only after approval of the protocol and ICF including Subjects instruction and Subjects calendar by the IRB/IEC. The approval letter or notice must contain the IRB name and identification number, meeting date, and sufficient information to identify the protocol and ICF form by name and number that were reviewed. PDI prior to study initiation, must receive a copy of the IRB/IEC approval letter.

The IRB used for this study will be:

Name: Advarra, Inc

Address: [name]

The IEC used for this study will be:

Name: Institutional ethics committee

Address: [name]

Subject confidentiality is strictly held in trust by the PI, the study staff, and PDI This confidentiality is extended to cover testing of biological samples in addition to the clinical information relating to participating subjects. Subject confidentiality and anonymity will be maintained at all times by removal of all identifiers from any data, clinical samples or documentation submitted for this study.

Any data collected meeting the definition of protected health information will be collected and maintained using the designated authorizations and following all privacy procedures as specified in the applicable health authority regulations.

PDI will maintain the security and confidentiality of all clinical study data received.

PDI clinical study databases will not be shared with any third party without the express written consent of the PI and/or Research facility.

15 Data Handling and Record Keeping

15.1 Completion of Case Report Forms

The PI or sub-investigator will review all CRF entries for completeness and accuracy. If a correction is required, a single line must be drawn through the error. The person making the correction will initial, date, and provide a reason for the error (if not self-evident).

The PI or sub-investigator must review and sign each CRF in a timely fashion following completion and make them available to the PDI study monitor for monitoring. Before acceptance, the monitor will review the CRFs to ensure accuracy and completeness. The original CRFs will be kept at the Research facility and electronic/scanned copies will be sent to PDI In addition, any data queries prepared after the original CRFs have been completed must be answered promptly.

15.2 Final Clinical Study Report

Final Clinical Study report will be produced by Research facility in collaboration with PDI team.

17.1 Study Summary

Study Procedures	Washout phase	Treatment Day
Initiation of consenting process	x	
Review study ICF	х	
Review Inclusion/ Exclusion Criteria	х	х
Review subject's instructions	х	
Subject signs ICF	х	
Visual skin assessment (groin region) and Inclusion/ Exclusion Criteria	х	x
Dispense subject kits	х	
Schedule for clipping/re-clipping, if needed, approximately 48-96 hours prior to treatment visit	x	
No bathing / showering 72 hours prior to treatment visit	x	
Mark test area, Collect baseline samples (treatment)		х
Apply test products		х
Visual skin assessment, within 30 seconds post-prep sample		х
Visual skin assessment, 10 minutes post-prep sample		х
Count Baseline (treatment) plates, determine qualification		х

17.2 Groin Diagram

17.3 Randomization Scheme Example

The randomization will be provided in a separate document.

Randomization number	Body Area	Product Left Side	Product Right Side	Site 1	Site 2	Site 3

17.5 Treatment Application Instructions

Investigational Product: Treatment A (Project X 26 mL)

Treatment Site Application Instructions – Groin

- 1. Weigh the applicator package and record the weight
- 2. Peel open package and remove applicator do not touch swab.
- 3. Hold the applicator with swab down.
- 4. Press down the antiseptic reservoir to release the antiseptic to the swab.
- 5. Wet the swab by repeated blotting against the treatment area until antiseptic is visible on the skin.
- 6. Thoroughly wet the treatment area with antiseptic using gentle back-and-forth strokes for two minutes.
- 7. Weigh the applicator package and record the weight
- 8. Allow antiseptic to completely dry (minimum of 3 minutes).
- 9. Do not blot or wipe dry.

Investigational Product: Treatment B (Project X 10.5 ml)

Treatment Site Application Instructions – Groin

- 1. Weigh the applicator package and record the weight
- 2. Peel open package and remove applicator do not touch swab.
- 3. Hold the applicator with swab down.
- 4. Press down the antiseptic reservoir to release the antiseptic to the swab.
- 5. Wet the swab by repeated blotting against the treatment area until antiseptic is visible on the skin.
- 6. Thoroughly wet the treatment area with antiseptic using gentle back-and-forth strokes for two minutes
- 7. Weigh the applicator package and record the weight
- 8. Allow antiseptic to completely dry (minimum of 3 minutes).
- 9. Do not blot or wipe dry.

Investigational Product: Treatment C (Project X 5.1 ml)

Treatment Site Application Instructions – Groin

- 1. Weigh the applicator package and record the weight
- 2. Peel open package and remove applicator do not touch swab.
- 3. Hold the applicator with swab down.
- 4. Press down the antiseptic reservoir to release the antiseptic to the swab.
- 5. Wet the swab by repeated blotting against the treatment area until antiseptic is visible on the skin.
- 6. Thoroughly wet the treatment area with antiseptic using gentle back-and-forth strokes for two minutes.
- 7. Weigh the applicator package and record the weight
- 8. Allow antiseptic to completely dry (Minimum of 3 minutes).
- 9. Do not blot or wipe dry.

Positive Control: Treatment D (Prevantics® Maxi Swabstick)

Treatment Site Application Instructions – Groin

- 1. Weigh the swabstick package and record the weight
- 2. Peel open package and remove swabstick do not touch swab.
- 3. Place one flat side of the foam tip within the pre-measured treatment area, and prep with back-and-forth repeated strokes for 60 seconds.
- 4. Turn the Maxi-swabstick over and repeat the procedure for 60 seconds
- 5. Do not apply swab beyond borders of marked skin areas by more than one swab width.
- 6. Weigh the swabstick package and record the weight
- 7. Allow the area to completely air-dry; approximately 90 seconds.
- 8. Do not blot or wipe dry.

17.6 Skin Irritation Rating Scale

Skin Irritation Scoring System			
Condition	Rating	Description	
	0	No reaction	
Erythema	1	Mild and/or transient redness limited to sensitive area	
Liyenema	2	Moderate redness persisting over much of the product-exposed area	
	3*	Severe redness extending over most or all of the product-exposed area	
	0	No reaction	
Edema	1	Mild and/or transient swelling limited to sensitive area	
Lacina	2	Moderate swelling persisting over much of the product-exposed area	
	3*	Severe swelling extending over most or all of the product-exposed area	
	0	No reaction	
Rash	1	Mild and/or transient rash limited to sensitive area	
110511	2	Moderate rash persisting over much of the product-exposed area	
	3*	Severe rash extending over most or all of the product-exposed area	
	0	No reaction	
Dryness	1	Mild and/or transient dryness limited to sensitive area	
Diyiless	2	Moderate dryness persisting over much of the product-exposed area	
	3*	Severe dryness extending over most of all of the product-exposed area	

^{*} A score of 3 in one or more of the conditions evaluated represents significant irritation and qualifies as an Adverse Event.

17.7 Confirmation of Release and Receipt of Study Materials Form

Study No: ER 19	/232		
Research facility	: EUROFINS EVIC PRODUCT TESTING R	OMANIA S.R.L.	
Quantity (Units)	Description	ID/Lot Number	Expiration Date
upplies Released to	Research facility by:		
	Sponsor Signature	gnature	
upplies Sent to Rese	arch facility (Date):		
upplies Checked and	l Verified by:		
	Signature		Date

Once the supplies have been verified and this form is signed / dated, a signature copy will be sent to the sponsor representative: [contact].

